11. STATISTICAL METHODS

The statistical analysis methods for this study are outlined in this section. Further details will be specified in the Statistical Analysis Plan.

11.1. Subject Information

The 2 phases of this study will be analyzed separately. When appropriate, all subjects who are treated with daratumumab may be combined together for comprehensive safety assessment.

Variables will be estimated by using descriptive statistics. Continuous variables will be summarized by using the number of observations (n), mean, standard deviation, median, minimum, and maximum, where n denotes the number of subjects with available data. Categorical variables will be summarized by using n and percentages, where the calculation of the percentages will be based on the number of subjects in the population (N) and the number of subjects with available data (n). Results will be presented by cohort as well as by all subjects combined.

The latest available measurements before study drug administration will serve as baseline values.

11.2. Sample Size Determination

Between 42 and 58 subjects will be enrolled in this study, depending on the number of dose levels included during dose escalation in Phase 1. It is estimated that the screen failure rate will be 25% and that between 56 and 78 subjects will be screened in order to enroll the expected number. The screen failure rate is estimated based on data from the ongoing GEN501 study.

No formal sample size determination was performed for Phase 1 of this study because a standard dose escalation study design of 3+3 subjects in each cohort was chosen for Phase 1. For Phase 2, It is assumed that lenalidomide + dexamethasone would achieve an ORR of 50% in the targeted population. With a two-sided alpha of 0.10 and assuming that the addition of daratumumab improves the ORR to 75%, a sample size of approximately 30 subjects would achieve 89% power to detect such a difference. If the addition of daratumumab can improve the ORR to 80%, this sample size would achieve 97% power to detect such a difference.

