
Secondary Objectives

- To evaluate the efficacy of daratumumab when given in combination with Len/Dex in subjects with relapsed or relapsed and refractory multiple myeloma.
- To evaluate the PK profile of daratumumab when given in combination with Len/Dex in subjects with relapsed or relapsed and refractory multiple myeloma.
- To assess the immunogenicity of daratumumab.

Hypothesis

No formal statistical hypotheses are planned to be tested.

OVERVIEW OF STUDY DESIGN

This is an open-label, dose-escalation, multicenter, Phase 1/2 safety study of daratumumab in combination with lenalidomide and dexamethasone (Len/Dex) in the treatment of subjects with relapsed or relapsed and refractory multiple myeloma. The dose escalation portion of the study (Phase 1) will be a standard 3 + 3 design and will evaluate daratumumab, at doses from 2 mg/kg up to a maximum of 16 mg/kg, in combination with Len/Dex in 28-day treatment cycles. The maximum tolerated dose (MTD) will be defined as the highest dose of the combination regimen at which less than 33% of subject's experience dose-limiting toxicity (DLT). A recommended Phase 2 dose (RP2D) will be determined during Phase 1. The MTD or any dose evaluated in the range of 2 to 16 mg/kg of daratumumab may be considered as the RP2D based on available safety, pharmacokinetic (PK)/pharmacodynamic, and efficacy data from Phase 1. The RP2D could be selected before escalation to or completion of the 16 mg/kg cohort. Once the RP2D is determined, the expansion (Phase 2) will open to further explore the safety and efficacy of the RP2D in approximately 30 subjects.

For Phase 1 and Phase 2 portions of the study, the first 2 treatment cycles will consist of weekly daratumumab infusions, totaling 4 infusions during each 28-day cycle. Cycles 3 through 6 will consist of daratumumab infusions administered every other week; Cycle 7 and all subsequent cycles will consist of monthly daratumumab infusions. The combination treatment may continue until the subject experiences disease progression or unacceptable toxicity, whichever comes first. Daratumumab may be continued until investigator's or sponsor's recommendation of discontinuation, the subject's decision to discontinue for any reason, or disease progression. In Phase 1 and Phase 2, if the subject must stop one component of the combination treatment (either daratumumab, lenalidomide or dexamethasone), the subject may

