The 2 phases of this study will be analyzed separately. When appropriate, all subjects who are treated with daratumumab may be combined together for comprehensive safety assessment. The latest available measurements before study drug administration will serve as baseline values.

Phase 1 follows a standard 3+3 design. For Phase 2, it is assumed that lenalidomide + dexamethasone would achieve an ORR of 50% in the targeted population. With a two-sided alpha of 0.10 and assuming that the addition of daratumumab improves the ORR to 75%, a sample size of approximately 30 subjects would achieve 89% power to detect such a difference. If the addition of daratumumab can improve the ORR to 80%, this sample size would achieve 97% power to detect such a difference. The proportion of subjects with response to treatment (stringent CR [sCR], CR, very good PR [VGPR], and PR) will be estimated. The quality of response (also including subjects who achieve MR) will be summarized. The proportions will be presented with corresponding exact 2-sided 95% confidence intervals. Duration of response, time to progression, and PFS will be estimated using Kaplan-Meier techniques.

Subject information variables will be estimated by using descriptive statistics. Continuous variables will be summarized by using the number of observations (n), mean, standard deviation, median, minimum, and maximum, where n denotes the number of subjects with available data. Categorical variables will be summarized by using n and percentages, where the calculation of the percentages will be based on the number of subjects in the population (N) and the number of subjects with available data (n). Results will be presented by cohort as well as by all subjects combined.

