3.2.2. Rationale for Study Design

In this Phase 1/2 safety study of daratumumab in combination with lenalidomide and low-dose dexamethasone (Len/Dex), a standard Phase 1 "3 + 3" design is appropriate to adequately observe DLTs associated with the regimen while not exposing an undue number of subjects to doses that may be subtherapeutic. The dose escalation phase of the study (Phase 1) will be followed by Phase 2, upon identification of recommended Phase 2 dose (RP2D). Approximately 30 subjects will be enrolled in Phase 2, which will allow for a greater degree of experience with the combination therapy at what is expected to be a therapeutic dose of daratumumab and Len/Dex.

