1.3. Statistical Hypotheses for Trial Objectives

For both two phases, the primary endpoint is adverse event; therefore, no formal statistical hypothesis testing is planned.

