1.4. Sample Size Justification

No formal sample size determination was performed for Phase 1 of this study because a standard dose escalation study design of 3 + 3 subjects in each cohort was chosen for Phase 1.

For Phase 2, it is assumed that lenalidomide + dexamethasone would achieve an overall response rate (ORR) of 50% in the targeted population. With a two-sided alpha of 0.10 and assuming that the addition of daratumumab improves the ORR to 75%, a sample size of approximately 30 subjects would achieve 89% power to detect such a difference. If the addition of daratumumab can improve the ORR to 80%, this sample size would achieve 97% power to detect such a difference.

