Key: CR = complete response; EBMT = European Group for Blood and Marrow Transplantation; FLC = free light chain; MR = minimal response; PC = plasma cell; PR = partial response; sCR = stringent complete response; VGPR = very good partial response.

Analysis Methods

ORR will be analyzed for all treated subjects in Phase 1, and for ITT and PP populations in Phase 2.

The number and percentage of patients in the following response categories will be tabulated by dose group and overall: sCR, CR, sCR + CR, VGPR, VGPR or better, PR, ORR, MR, ORR + MR, stable disease (SD), progressive disease (PD), and not evaluable (NE). For each of the above categories, two-sided 95% exact confidence interval (CI) will also be presented.

Subgroup analyses as specified in Section 2.4 will also be performed...

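### Does sizing Phase 2 at two-sided alpha 0.10, while reporting ORR with an exact 95% interval and planning no test, overstate the power?

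*Protocol*

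**What the plan says.** The sample-size paragraph appears in the Protocol Synopsis (Statistical Methods), Protocol 11.2 and SAP 1.4. It takes 50% as the ORR expected from lenalidomide and dexamethasone alone. SAP 1.4 reads: "With a two-sided alpha of 0.10 and assuming that the addition of daratumumab improves the ORR to 75" per cent, and Protocol 11.2 concludes that "a sample size of approximately 30 subjects would achieve 89% power to detect such a difference". For an ORR of 80% the stated power is 97%. The test behind these figures is not named.

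On testing, the Synopsis and Protocol 2.2 state: "No formal statistical hypotheses are planned to be tested". SAP 1.3 gives the reason, that the primary endpoint is adverse events, and says that "no formal statistical hypothesis testing is planned". SAP 5.1.1, on the level of significance, also rules out formal tests.

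On reporting, the Synopsis and Protocol 11.4 say: "The proportions will be presented with corresponding exact 2-sided 95% confidence intervals". SAP 5.2 says: "The number and percentage of patients in the following response categories will be tabulated by dose group and overall". The categories run from stringent complete response to progressive disease and not evaluable, and for each a "two-sided 95% exact confidence interval (CI) will also be presented".

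Protocol 3.2.2 gives a second, qualitative reason for about 30 patients, "which will allow for a greater degree of experience with the combination therapy". Protocol 9.3 lists response rate as a secondary endpoint.

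**The concern.** Power has meaning only relative to a criterion, and the criterion implied by the sample-size text, two-sided 0.10, is used in no planned analysis. The only interval planned for ORR is a 95% interval, which is stricter. Phase 2 has a single cohort and no control arm, so 50% is the only benchmark the plan offers for ORR. It is natural to look at whether the reported interval clears it.

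A reader who took 89% and 97% as the chance of that happening would be too optimistic. The sample-size text does not say that the figures are for planning only, and it is the only numerical basis for the Phase 2 size. At stake would be a sizing rationale that promises more than the reported analysis can deliver.

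**Working it through.** **Inputs.** From Protocol 11.2 and SAP 1.4: n = 30 (the text says approximately 30), reference ORR p0 = 0.50, alternatives 0.75 and 0.80, two-sided alpha 0.10, so 0.05 in the upper tail. From Protocol 11.4 and SAP 5.2: exact two-sided 95% interval. Assumption, because no test is named: an exact one-sample binomial test.

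**Formula.** With X responders among n, P(X ≥ c | p) = Σ (k = c to n) C(n,k) p^k (1 − p)^(n−k). The cut-off c is the smallest count whose upper tail at p0 is within the allowed size. Power is the same sum at the alternative ORR.

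**Step 1: the plan's own figures.**
- P(X ≥ 20 | 0.50) = 0.0494, which is within 0.05.
- P(X = 19 | 0.50) = C(30,19)/2^30 = 54,627,300/1,073,741,824 = 0.0509. So P(X ≥ 19 | 0.50) = 0.0494 + 0.0509 = 0.1003, too large. The cut-off is 20.
- Power: P(X ≥ 20 | 0.75) = 0.8943 and P(X ≥ 20 | 0.80) = 0.9744.

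These match the stated 89% and 97%. A normal approximation using the null variance gives 0.8967 and 0.9799, which round to 90% and 98%, so the exact test is the better match.

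**Step 2: the 95% interval read against 50%.** The exact (Clopper-Pearson) lower limit at x responders exceeds 0.50 when P(X ≥ x | 0.50) is below 0.025.
- P(X = 20 | 0.50) = 30,045,015/1,073,741,824 = 0.0280, so P(X ≥ 21 | 0.50) = 0.0494 − 0.0280 = 0.0214. The count needed is 21.
- The interval is 47.2% to 82.7% at 20/30, and 50.6% to 85.3% at 21/30.

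| Criterion, n = 30 | Responders needed | ORR 75% | ORR 80% |
|---|---|---|---|
| Two-sided alpha 0.10 | 20 | 89.4% | 97.4% |
| 95% lower limit above 50% | 21 | 80.3% | 93.9% |
| Difference = P(X = 20) | exactly 20 | 9.1 points | 3.5 points |

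**Step 3: the approximate sample size.** The documents give no range. If n = 28 to 32 is assumed, the 0.10 criterion is met with probability 83% to 89% (ORR 75%) and 95% to 97% (ORR 80%). The 95% reading gives 71% to 80% and 89% to 94%. Much of that spread is binomial discreteness: for the 95% reading at ORR 75%, n = 32 gives 73.7%, less than the 80.3% at n = 30.

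**Step 4: which row the plan uses.** The first row is the one the sample-size text describes, with its alpha in the same sentence as the power. The second needs a rule that the 95% interval must exclude 50%, and neither document contains one. SAP 5.2 attaches the same interval to minimal response, stable disease, progressive disease and not evaluable, for which 50% has no meaning. It is a reporting format.

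**The case for a change.** The strongest case for a change is that a power statement carrying an alpha sits beside several statements that nothing will be tested, with no sentence to connect them. SAP 5.2 places ORR under a primary efficacy heading, and SAP section 3 says the data cut is meant to support a licence application, so outside readers may rely on the ORR result and on its sizing. At 20 of 30 the sizing criterion is met while the reported interval still includes 50%. A short label would cost almost nothing.

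The facts in this stand: no analysis uses 0.10, and the sample-size paragraphs do not call the figures supportive. The inference does not follow. To be misled, a reader must disregard the alpha in the power sentence and apply the result to an interval that the text never links to it. In the SAP the statement that nothing is tested, with its reason, comes immediately before the power paragraph, so the figures can hardly be taken for anything but planning figures.

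Sizing at one error rate and describing at the conventional 95% level is an acceptable choice for a single-arm expansion cohort. Printing 80% and 94% beside the stated figures would bring in a success threshold that the plan disclaims.

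**Conclusion.** No change follows. The stated 89% and 97% are correct for the alpha given, assuming an exact one-sample binomial test and n = 30. The figures of 80% and 94% answer a different question and should not be presented as the plan's true power.

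The practical reach is one outcome, exactly 20 responders of 30. There the reported interval is the more cautious of the two, so the mismatch cannot make a result look stronger. The responder count is tabulated, so a reader can make either comparison. No decision, error rate or stopping rule depends on it.

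Nor can rewording affect the size of the study. The Synopsis and the SAP introduction record that, by Amendment 7, every subject had received at least 12 months of study drug or had discontinued. A clause calling the power a planning figure would do no harm, but it would add little to what Protocol 2.2 and SAP 1.3 already say, and the analysis and its conclusion would be the same.

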11.3. Analysis Sets

For Phase 1, one analysis population, the safety population, is defined, which includes all subjects who are exposed to the study drugs (daratumumab, lenalidomide, and dexamethasone). For Phase 1, the safety population will be used for all efficacy and safety analysis.

For Phase 2, three analysis populations are defined:

- Intent-to-Treat (ITT), defined as all subjects enrolled in the study in Phase 2
- Safety, defined as all subjects exposed to the study drugs (ie, daratumumab, lenalidomide, and dexamethasone) in Phase 2
- Per-Protocol (PP), defined as all subjects included in the ITT population excluding those
 who had deviations from the protocol that might affect the assessment of response to
 treatment

For Phase 2, the ITT population will be the primary analysis population for all efficacy analyses. The Safety population will be used for all safety analyses. If the ITT and Safety populations are identical, only the ITT population will be used.

The PK evaluable population will be analyzed, which includes all treated subjects who have an evaluable PK profile. The PP population will be used for efficacy as sensitivity analyses. If the difference between the PP and ITT populations is less than 4 subjects, the PP analysis will not be performed.

11.4. Efficacy Analyses

Response to treatment will be determined by the sponsor in accordance with the guidelines provided in Attachment 5. The proportion of subjects with response to treatment (stringent CR [sCR], CR, very good PR [VGPR], and PR) will be estimated. The quality of response (also including subjects who achieve MR) will be summarized. Subjects for whom response cannot be evaluated will be categorized as not evaluable. A determination of not evaluable will count as nonresponse to treatment. The proportions will be presented with corresponding exact 2-sided 95% confidence intervals.

Duration of response, time to progression, and PFS will be estimated using Kaplan-Meier techniques. Data for these variables will be censored in accordance with the FDA guidance on clinical study endpoints for the approval of cancer drugs and biologics (FDA 2011).

11.5. Pharmacokinetic Analyses

Pharmacokinetic analyses will be performed on the pharmacokinetic-evaluable population, defined as subjects who have received one dose of daratumumab and at least one post infusion sample. All serum concentrations below the lowest quantifiable concentration or missing data will be labeled as such in the concentration data presentation. Concentrations below the lowest quantifiable concentration will be treated as zero in the summary statistics. All subjects and samples excluded from the analysis will be clearly documented in the study report.

Phase 1: The PK variables, AUC, C_{max} , C_{min} , T_{max} , CL, V, and t1/2, will be estimated by using noncompartmental methods. The AUC will be calculated separately for Cycles 1 and 2, and extrapolated to infinity. Geometric means will be plotted together for comparison of dose cohorts, and individual subject PK profiles will be plotted with both absolute and log-transformed values.

Phase 2: Descriptive statistics will be used to summarize daratumumab serum concentrations at each sampling time point and pharmacokinetic parameters of daratumumab such as C_{min} and C_{max} . If sufficient data are available, then other pharmacokinetic parameters may be calculated, including but not limited to CL and V.

If sufficient data are available, population PK analysis of serum concentration-time data of daratumumab may be performed and the analysis may include data from other studies. If the population PK analysis is conducted, details will be specified in a population PK analysis plan, and the results of the analysis will be presented in a separate report.

11.6. Pharmacokinetic/Pharmacodynamic Analyses

If sufficient data are available, pharmacokinetic/pharmacodynamic modeling may be performed, including exploring the relationship between serum concentrations of daratumumab and endpoints of clinical efficacy. If performed, details and results of the analysis will be presented in a separate report.

11.7. Subgroup and by Center Analyses

Analyses will be performed for the following subgroups:

- Subjects with relapsed multiple myeloma versus subjects with relapsed and refractory multiple myeloma
- Subjects by number of prior therapies

The number of subjects per site is expected to be very low; therefore, no by-center analyses are planned.

11.8. Exploratory Modeling

Exploratory univariate modeling will be used to investigate preliminarily relationships between select efficacy and safety variables and possibly explanatory variables.

A model of the worst toxicity will be attempted to potentially provide a rationale for dose selection in subsequent studies. This model is included in Attachment 6.

11.9. Immunogenicity Analyses

The incidence of antibodies to daratumumab will be summarized for all subjects who receive a dose of daratumumab and have appropriate samples for detection of antibodies to daratumumab.

11.10. Biomarker and Pharmacogenomic Analyses

Biomarker studies are designed to identify markers predictive of response (or resistance) to daratumumab. Analyses will be stratified by clinical covariates or molecular subgroups using the appropriate statistical methods (eg, parametric or non-parametric, univariate or multivariate, analysis of variance [ANOVA], or survival analysis, depending on the endpoint). Correlation of baseline expression levels or changes in expression levels with response or time-to-event

endpoints will identify responsive (or resistant) subgroups in addition to genes and pathways attenuated following treatment with daratumumab.

Any biomarker, pharmacodynamic, and pharmacogenomic measures will be listed, tabulated, and where appropriate, plotted. Subjects will be grouped by prescribed dose. As this is an open-label study with an active control treatment, statistical analyses will be done to aid in the understanding of the results. Correlation of response and pharmacogenomic measures will be explored.

Results of biomarker, pharmacodynamics, and pharmacogenomic analyses may be presented in a separate report. Planned analyses are based on the availability of clinically valid assays and may be deferred if emerging study data show no likelihood of providing useful scientific information.

11.11. Safety Analyses

The verbatim terms used in the CRF by investigators to identify adverse events will be coded using the Medical Dictionary for Regulatory Activities (MedDRA). All reported adverse events with onset during the treatment phase (ie, treatment-emergent adverse events, and adverse events that have worsened since baseline) will be included in the analysis.

The number and percentage of subjects with treatment-emergent AEs will be summarized according to intensity by using the CTCAE v4.0, drug relationship, and outcome. Laboratory data will be summarized and descriptive statistics will be calculated. Changes in vital sign measurements, physical examination findings, and ECOG performance status will be summarized. Safety laboratory variables will be presented in figures (values versus time) and summarized by value and change from baseline (both absolute and relative).

11.12. Interim Analysis

Results from Phase 1 and Phase 2 will be presented separately. Data from Phase 1 will be analyzed when the MTD has been reached or dose escalation has been stopped. No formal interim analyses that require adjustments of type 1 or 2 errors are planned. However, as part of the preparations for subsequent studies, exploratory analyses of subsets of data may be performed.

11.13. Data Monitoring Committee

An IDMC will be established and have their first meeting before study start (first subject screened). At this meeting, the IDMC will decide the future format and the degree of the information they need in order to monitor safety.

The functions and responsibilities of the IDMC will be described in the IDMC Charter, which will be approved by the IDMC.

The IDMC will receive a package of safety data, including all reported AEs and laboratory data, after each cohort has completed the first cycle of treatment. The IDMC will receive a report of any SAE immediately after review of the event by the sponsor.

Subjects will be enrolled in cohorts of 3 subjects per dose level. The "3 + 3" rules for dose escalation will be applied. However, if the study sites have identified 4 eligible subjects to start a new dose level, all 4 subjects may be enrolled. For each cohort, the IDMC will evaluate aggregate safety data for the 3 subjects in order to recommend whether it is safe to escalate to the next dose level. Before the IDMC review of safety data, at least 3 subjects in a cohort must receive at least 4 full infusions of daratumumab in combination with Len/Dex. The third subject in the cohort must have received all 4 full doses of daratumumab, and data from an observation period of 6 days after the last infusion must be available for the IDMC to review. Dose escalation or de-escalation will follow these rules:

- An initial cohort of 3 subjects will be enrolled at any new dose level, when escalation from the previous dose level has been accepted by the IDMC.
- If a subject at any dose level experiences a DLT, the cohort will be expanded by up to 3 additional subjects, or until a second subject experiences a DLT.
- If, however, no additional DLTs are reported at this dose level, dose escalation may take place to the next planned dose level, or to an intermediate dose level as recommended by the IDMC and approved by the sponsor.
- If no DLTs are experienced by the first 3 subjects at any dose level, the IDMC or sponsor may decide to add 3 more subjects at this dose level based on the need for additional safety data before an escalation can take place.
- If 2 or more subjects out of 6 or less subjects experience DLTs, additional subjects must be included at the previous dose level or at an intermediate dose level as recommended by the IDMC and approved by the sponsor.
- The MTD will be defined as the highest dose level where no subjects or 1 subject out of 6 subjects experiences a DLT.

Noncompliance with the protocol-defined requirements for infusion of the study drug may influence the evaluation of DLTs by the IDMC.

In the dose escalation/de-escalation part, the MTD and/or RP2D will be decided by the sponsor, based upon recommendations by the IDMC and after review of the aggregated safety data.

At least every 6 months, the IDMC will evaluate safety data from this study, including the occurrence of new cancers as noted during the Safety Follow-up Period, and provide a recommendation as to whether the study should continue based on evaluation of these safety data and the reported benefits of daratumumab treatment. The IDMC will no longer be evaluating safety data after the primary analysis.

Minutes from the IDMC meetings will be shared with the regulatory agencies.

There are no current plans to establish an Independent Response Committee for this early-phase study. Response to treatment will be evaluated by the coordinating investigator in collaboration with the sponsor.

